#### *Home-base testing*

We estimate that the volunteers will test 10 suspected case of malaria each month. Given that there are 7 communities, we have  $(7 \times 10 \times 24) = 1680$  RDTs. Total cost for home based testing is given by  $\$0.63 \times 1680 = \$1,058.4$ .

Total cost of RDTs  **$1,058.4 + 18,900 = 19,958.4$**

### *Anaemia*

Anaemia is estimated to be 27% in under five children. It is estimated that 30% (1350) of the population of Pakro is made up of children under five years, giving  $1350 \times 0.27 = 365$  anaemic cases. Assuming a 5% reduction after the first intervention, in the second intervention we will target 22% aiming at reducing it to 17% while in the third intervention we aim to reduce it to 12%. For cost purposes we

will maintain it at 12% after the third intervention. Hemocue photometer = \$1000, total number of micro cuvettes =  $365 + 297 + 4(230) = 1,582$ . One cuvette cost \$1, giving  $(\$1 * 1,582) = \$1,582$ .

Total cost for anaemia is **\$2,582**

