### **Data collection**

Following consent, blood will be drawn from a finger prick. All participants will be tested for the presence of malaria parasites using RDTs. Additionally, blood will be collected on filter paper to enable molecular characterization in case treatment failure is observed in a given patients as explained above. All samples will be stored at NMIMR. To test for anaemia (for children in the cohort study only), a portable automated Hemocue photometer will be used to determine the concentration of Haemoglobin. Anaemia in this study is defined as Hb levels less than 10g/dl. Children with severe anaemia (Hb less than 7g/dl) will be referred to the Pakro Health Centre for follow up. **At evaluation, family members will be asked questions on how much they used to spend on malaria before the intervention and how much they have spent after. Malaria case management records before and after the intervention will be consulted, firstly to determine the change in prevalence and also for cost benefit analysis purposes.**

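### The haemoglobin cuvette count follows expected anaemic under-fives, not cohort children tested; with six measurements 1,582 cuvettes fall 28% to 43% short

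*Protocol*

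**What the plan says.** The Data collection section defines who is tested: "To test for anaemia (for children in the cohort study only), a portable automated Hemocue photometer will be used". Anaemia is a haemoglobin below 10 g/dl, and children below 7 g/dl are referred to the health centre. The section does not say at which surveys haemoglobin is measured.

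Study participants and Sample size set the cohort at 460 children aged 6 months to 15 years. This is 368 inflated for 10% loss to follow-up and 10% non-response. Study Design places the cohort surveys at baseline and before each later treatment round. The budget explanation (Intervention team members) gives six rounds over two years.

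The budget's Anaemia section works from a different group. It states that "Anaemia is estimated to be 27% in under five children" and that "30% (1350) of the population of Pakro is made up of children under five years", and multiplies the two to obtain 365 anaemic cases. For the next rounds it says "in the second intervention we will target 22% aiming at reducing it to 17" per cent, with 12% as the aim of the third round, and adds that for costing it "will maintain it at 12% after the third intervention". The "total number of micro cuvettes" is then given as "365 + 297 + 4(230) = 1,582", at $1 each. With a $1,000 photometer this makes an anaemia line of $2,582.

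**The concern.** A cuvette is used for each child measured, whatever the result. Multiplying by prevalence gives the number of anaemic children the test would find, and that cannot be known before testing. The population differs as well: all under-fives in the seven communities rather than the cohort up to age 15.

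The same budget uses the right unit elsewhere. Rapid tests are counted per person tested (5,000 per round for 4,500 people), and treatment courses per expected case. The Anaemia section applies the treatment logic to a diagnostic consumable.

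If the purchase followed this line and haemoglobin were measured throughout, the stock would be used up before the last surveys. Later haemoglobin data would be incomplete, and severely anaemic children who were not tested could not be identified for the referral the protocol provides.

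**Working it through.** **Inputs.** 1,350 under-fives; prevalences 27%, 22%, 17% and 12%; 1,582 cuvettes at $1; photometer $1,000 (all budget, Anaemia). Cohort of 460, inflated from 368, and 116 children in each of four age groups (Sample size). Six rounds (Intervention team members). Budget total before and after contingency: $93,508.78 and $98,184.209 (Budget).

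**1. Reproduce the plan's figure.**
- Round 1: 1,350 × 0.27 = 364.5, rounded to 365
- Round 2: 1,350 × 0.22 = 297
- Rounds 3 to 6: 1,350 × 0.17 = 229.5, rounded to 230 each
- Total: 365 + 297 + 4 × 230 = 1,582, as stated

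**2. Check it against its own text.** If 12% holds after the third round, rounds 4 to 6 take 1,350 × 0.12 = 162 each. The total is then 365 + 297 + 230 + 3 × 162 = 1,378 (1,377 without rounding). The conflict concerns rounds four to six. Resolving it in favour of the text would lower the count and leave the wrong basis in place.

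**3. Count by children tested, assuming six surveys.** Needed = children per survey × 6; shortfall = needed − 1,582.

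| Children per survey | Needed | Shortfall | Share of tests |
|---|---|---|---|
| 368 (after planned losses) | 2,208 | 626 | 28% |
| Linear fall from 460 to 368 (mean 414) | 2,484 | 902 | 36% |
| 460 (full cohort) | 2,760 | 1,178 | 43% |
| 464 (4 × 116) | 2,784 | 1,202 | 43% |

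**4. When one common stock runs out.**
- At 460 per survey: three surveys use 1,380, leaving 202 for the fourth and none for the fifth and sixth.
- At 368 per survey: four surveys use 1,472, leaving 110 for the fifth and none for the sixth.

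**5. Dependence on the number of measurements.**
- Three surveys: at most 3 × 460 = 1,380 (1,392 with 464 children), so 1,582 suffices.
- Four surveys: 1,472 (368 children) is covered; 1,840 (460 children) is 258 short, or 14%.
- Six surveys: short throughout the range in step 3.

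**6. Cost.** The shortfall costs $626 to $1,202. The contingency is 98,184.209 − 93,508.78 = about $4,675.

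**The case against.** The strongest reply is that the size of the shortage rests on something the protocol does not say. Data collection restricts haemoglobin to the cohort but gives no frequency, and the six scheduled surveys are described as prevalence surveys. With three or fewer measurements the stock is sufficient. This stands, and it makes the shortage conditional. The support for six is that the Anaemia section itself provides cuvettes for six rounds; no three-survey haemoglobin plan appears in the protocol.

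A reader might infer a flat 43% shortage. The protocol does not support that, because 460 already includes the allowance for loss and non-response. The figure is an upper value for a cohort of 460, with 28% at 368 children per survey.

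A reader might also set 365, 297 and 230 against 460 and infer that every survey, baseline included, is short by 95, 163 and then 230. Those terms belong to a costing sum that yields one total and one price. Nothing rations cuvettes by survey, and as one stock they cover baseline and the next two surveys in full.

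Perhaps only cohort under-fives are meant. Two age groups of 116 over six surveys would need 232 × 6 = 1,392, which is covered. But Data collection sets no such age limit, and the sum starts from 1,350 children, not 232.

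Finally, this is a small budget line, and anaemia appears in none of the objectives or expected outcomes. That is a fair limit on its importance. It does not make the count right, because the line sets the supply for a measurement the protocol specifies and links to a referral.

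**Conclusion.** The count is wrong as written in unit (expected cases instead of children tested) and in population (community under-fives instead of the cohort). It also contradicts its own 12%. None of these depends on how often haemoglobin is measured.

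The size does. Given haemoglobin at all six cohort surveys and 368 to 460 children each time, 1,582 cuvettes fall short by 626 to 1,178, or 28% to 43% of the tests, and the stock is exhausted in the fifth or fourth survey respectively. The consequence is incomplete haemoglobin data late in the study and possible missed referrals. The protocol gives no rate of severe anaemia from which to size the latter. The malaria prevalence outcome does not use these data and is not affected.

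**What to change.** 1. In Data collection, state at which cohort surveys haemoglobin is measured, and whether the separate evaluation phase includes a measurement.
2. In the budget's Anaemia section, replace the calculation from anaemic under-fives with cohort children × those surveys. This also removes the 17% versus 12% conflict. For six surveys of 460 children: 2,760 cuvettes, $2,760, and an anaemia line of 1,000 + 2,760 = $3,760. If 464 are enrolled: 2,784 cuvettes and $3,784.
3. Carry the new line into the Budget table and its total.

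The added cost is at most about $1,200 for six surveys, within the stated contingency of about $4,675. It should be settled before procurement. No anaemia threshold or referral rule needs to change.

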## Treatment

### Survey

The population of the targeted communities is estimated at 4500 people. We estimate 50% prevalence in the first intervention. Assuming a 15% reduction after the first intervention, the second intervention will target 35% prevalence which is expected to drop to 25%. After the third intervention we expect the prevalence to drop to 15% further to 10% after the fourth intervention. The 10% will be used as the prevalence over the next one year. As prevalence decreases the number of cases treated also decrease and consequently the cost. In the course of the different intervention we estimate that we will treat the following number of cases – first intervention  $(0.5 * 4500) = 2,250$ , second intervention  $(0.35 * 4500) = 1,575$ , third intervention  $(0.15 * 4500) = 675$  people. Beginning from the forth intervention we estimate a prevalence of 10% for remaining interventions giving  $(0.1 * 4500) = 450$  cases. Given that after the fourth intervention we have two more interventions, this give us  $(450 * 2) = 900$  cases. The total number of cases to be treated over two years is obtained by adding  $(2250 + 1575 + 675 + 450 + 900)$  cases = 5,850 cases. The course of treating one case is estimated at \$1 giving a total of **\$5,850**.

### *Home-based management of malaria*

We estimate that an average of 5 cases are additionally identified and treated in each community by the volunteers each month over the two years. This gives  $7 * 5 * 24 = 840$  cases. This will give an additional of  $840 * \$1 = \$840$ .

Total cost of treatment =  $(\$5,850 + \$840) = \$6,690$

## Consumable

Cost of consumable required such as gloves, safety boxes, silica gel, filter paper and PCT reagents will cost **\$2,024**. PCR will only be considered in case of treatment failure.

### **Incentive to children enrolled in the study**

It is estimated that children under five years make up 30% of the population of Pakro sub district. This gives  $(0.3 \times 4500)$  1350 children. We will be giving a token of a biscuit pack worth \$0.25 to each under five child tested. The adults will not be included in this package as the free treatment is already a good incentive for the community. Cost of incentives for children  $\$0.25 \times 1350 = \$337.5$  per survey. The 6 surveys will cost  $\$337.5 \times 6 = \$2,025$

### **Communication Cost**

This is to enable constant communication with the field team. The PI will work closely with the team in the field for update on home-base management and follow up of treated cases. This is to ensure that adverse effects are captured on time. Stockouts will be communicated through SMS. Each volunteer will be given a monthly communication credit of \$1.26 over two years ( $\$1.26 \times 14 \times 24 = \$423.36$ ) while the PI will require  $\$30.24 \times 24 = \$725.76$ . This gives a total communication cost over the two years of **\$1,149.12**.

### **Field bags**

Each team member will be given a bag to carry study material. We have 17 team members. Each bag will cost \$30. Therefore we have  $17 \times \$30 = \$510$ .

### **Community Entry**

We will need to introduce the study to the local authorities. This will be done through meetings and durbars with the chiefs. This is to facilitate community understanding and ownership of the project. Each of the chiefs will be provided a gift worth \$10. There are 7 community heads giving  $(7 \times \$10) = \$70$ .

### **Home-based management of malaria**

Following each intervention, volunteer workers are required to implement the home-base management of malaria between surveys. This is to clear residual as well as missed cases of parasitaemia in the community. Two volunteers from each of the communities (14 in total) who are already involved in IPT in children will carry out

this task. Each volunteer will receive an allowance of \$25.15 every three months. For a total of 6 interventions we have  $14 * \$25.15 * 6 = \$2,112.6$

### **Longitudinal Cohort study**

The PI and research assistant will spend one week in the community before each intervention administering the questionnaire to children enrolled in the cohort study. This will give a total of ( $6 * 7 = 42$  days) per person. The cost is as follows (Drivers ( $\$25.15 * 42 = \$1,056.3$ ), 1 Research Assistant = ( $\$30.18 * 42 = \$1,267.56$ ), PI ( $\$37.73 * 42 = \$1,571.56$  giving a total of **\$3,895.5**)

### **Personnel**

Personnel cost will be broken into censors, surveys and monitoring cost. During each of these activities in the field, the personnel will be paid a daily allowance.

#### *Household Census*

This will be undertaken by 17 personnel in 7 days (14 community volunteers, PI, 1 research Assistant and 1 driver). The PI, the research assistant and the driver will spend an extra one day to plan the census. During the census we will be supervising. We estimate that each volunteer will register an average of 46 people each day. Each of the team members will receive a daily allowance calculated as follows - volunteers ( $\$5.04 * 14 * 7$  days) =  $\$493.92$ , the driver ( $\$25.15 * 8$ ) =  $\$201.2$ , Research assistant ( $\$30.18 * 8$ ) =  $\$241.44$  and the PI ( $\$37.73 * 8$ ) =  $\$301.84$  giving a total of **\$1,238.4**

#### *Intervention*

A total of 17 personnel will be involved in the interventions which will be conducted every four months giving a total of 3 interventions per year and 6 over a two year period. The interventions will last 12 days. Each volunteer will spend a total of 72 intervention days ( $6 * 12$ ) over the two years in the field. The PI, research assistant will spend 6 extra days planning each intervention in the field. The cost is as follows – volunteers ( $\$5.04 * 72 * 14$ ) =  $\$5,060.16$ , Drivers ( $\$25.15 * 78$ ) =  $\$1,961.7$ , 1 Research Assistant = ( $\$30.18 * 78$ ) =  $\$2,354.04$ , PI ( $\$37.73 * 78$ ) =  $\$2,942.94$  giving a total of **\$12,318.61**.

### *Training*

A three days training will be organized for the volunteers before the interventions begins. To take part in the training will be 17 volunteers, two resource persons from the district health service will provide the training, the PI, a research assistant and the driver. This cost will include Transport for participants ( $\$2.5*20*3 = \$150$ ), Food ( $\$3*20*3 = \$180$ ), resource persons = ( $\$37.73*2*3 = \$224.22$ ), PI ( $\$37.73*3 = 112.11$ ), research assistant ( $\$30.18*3 = \$90.54$ ), driver ( $\$25.15*18 = 75.45$ ).

*The total cost for the training is \$832.32*

### *Monthly Monitoring visits*

We will undertake field visits to the study area every month to monitor progress, each lasting 2 days. This is to verify that the volunteers are doing the right thing, discuss challenges faced as well as replenish their stocks of RDT and ACTs. Each visit will last two days. Three persons will be involved, the PI, one research assistant and a driver. Since 6 of the 24 months will be involved in the surveys, the monitoring will take place over the 18 remaining months. The cost is calculated as follows - driver ( $\$25.15*18 = \$452.7$ , 1 Research Assistants ( $\$30.18*18 = \$543.24$ , and the PI ( $\$37.73*18 = \$679.14$  giving a total of **\$1675.08**

The total personnel cost is **\$15,232.09**

### **Data mining from the hospital records**

The registers of the Health Centre will be consulted and data will be extracted to study the trends of malaria admissions in this area over the last 10 years at baseline. Then after one year and at evaluation, another study of record will be conducted. This will require research assistants or a master student. This is estimated at **\$2500**.

### **Transportation**

Transport will involve hiring of the vehicle and fuel cost. From Accra to Pakro is 44.8Km (i.e. 89.6km in and out). There will be an initial trip to censor the area, 6 intervention trips of 12 days each, 16 monitoring trips of two days each over a two year period.

### *Mapping of the households and identification of people*

This will involve one trip of 7 days. As it involves going to all the households we estimate 20Km per day. This gives us  $89.6\text{Km} + (7*20\text{Km}) = 226.6\text{Km}$

### **Surveys**

We estimate to cover 10Km each day within the Pakro sub district during the surveys ( $12\text{days}*10\text{Km} + 89.6\text{Km interventions} = 249.6\text{Km for each intervention}$ ). We will be conducting 6 interventions which gives us  $249.6\text{Km}*6 = 1,497.6\text{Km}$

### **Monitoring visits**

Six of the project months will involve the intervention and therefore monitoring will occur over 18 months within the study period. This will involve the PI going to the field and meeting with the volunteer and replenishing their stocks workers. We estimate to cover 15Km in addition to the 89.6Km (in and out) for each trip giving a distance of  $104.6\text{Km}$ . Total distance during monitoring is  $104.6\text{Km}*18 = 1,882.8\text{Km}$

Total distance to be covered =  $(226.6 + 1,497.6 + 1,882.8) \text{ km} = 3,607\text{Km}$

### **Car Hiring Cost**

Currently, the cost for the use of NMIMR vehicle stands at \$0.76 per Kilometer. The total cost for hiring NMIMR cars is  $3,607 * \$1 = \$3,607$ .

### **Fuel Cost**

We estimate to use \$300 worth of fuel for each trip undertaken. Given that we are going to undertake 6 interventions, 18 monitoring and 1 censor visit, which gives  $(6+18+1)*\$300 = \$7500$

Total transport cost =  **$\$3,607 + \$7,500 = \$10,567$**

### **Rechargeable lamps**

Since these are rural communities and people are involved in different daily activities, work would have to start very early in the morning and extend into the night in order to reach out to a greater portion of the community as most of them will go out very early and come back late. Seven rechargeable lamps are therefore required at \$17.64 each giving a total of  **$\$123.48$** .

### **Statistical analysis**

The statistician at NMIMR will enter the household data into software and conduct analysis for 20 working days at \$150 a day, giving a total of **\$3000**.

### **Conference and publications**

The findings from this study will be disseminated through conferences, workshops and meetings with stakeholders. The PI is also expected to undertake some hands-on training on economic evaluation and cost benefit analysis.

**Consent Form** (Attached)

**Assent Form and Parental Consent Form** (Attached)

**Data Collection Instruments** (Attached)
